9.4.3 ANALYSIS OF THE SECONDARY ENDPOINT(S)

Secondary analyses will be performed in the ITT population on data from the DBP as follows:

- **RR50 (Key Secondary Efficacy Endpoint):** The proportion of participants experiencing a monthly (28 days) focal seizure frequency improvement from baseline of $\geq 50\%$ will be compared using a logistic regression model with baseline monthly (28 days) focal seizure frequency, region, background use of CYP3A4 inducer medication and treatment included as factors. Pairwise comparisons will be performed to characterize the dose response. Odds ratios and their 95% confidence intervals will be calculated for each comparison.
- **Stability of Weekly Seizure Frequency:** Within study arm, the absolute and percent change in weekly focal seizure rate will be calculated for every week of the treatment period and a linear test for trend will be evaluated and estimated to determine whether there is an average increase or decrease over time. A quadratic and spline effect may also be estimated for each dose, if the linear model appears inadequate for the data.
- **Clinical and Patient Global Impression of Change:** Change scores in each dose group will be compared to placebo using an ANCOVA, including for rank of baseline seizure frequency, region, and background use of CYP3A4 inducer medication. Estimated medians, and Hodges-Lehman estimates statistics for differences, will be calculated.

Analysis detail on statistical testing for secondary endpoints will be provided in the SAP.

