3 OBJECTIVES AND ENDPOINTS

OBJECTIVES	ENDPOINTS
Primary	
To assess the efficacy of XEN1101 compared to placebo on focal seizure frequency in adults with focal epilepsy taking 1 to 3 AEDs in the double-blind period (DBP).	
 Median percent change (MPC) in monthly (28 days) focal seizure frequency from baseline to DBP for XEN1101 versus placebo.
To assess the safety and tolerability of XEN1101 in adults with focal epilepsy taking 1 to 3 AEDs in the DBP.	
In the DBP:
 
 Severity and frequency of associated AEs/serious adverse events (SAEs). Clinically significant changes in clinical laboratory findings. Clinically significant changes in 12-lead ECG. Increase in suicide risk as assessed by the C-SSRS including increase in suicidal thoughts or an attempt. Clinically significant changes in vital signs including blood pressure, pulse, or weight. Clinically significant changes in urological symptoms including retention as measured by the American Urological Association (AUA) Symptom Index.
Secondary	
To evaluate the 50% XEN1101 response rates in comparison to placebo in the DBP.	
 Responders are defined as patients experiencing $\geq 50\%$ reduction in monthly (28 days) focal seizure frequency from baseline compared to DBP.
To evaluate trends in focal seizure frequency over time in the DBP.	
 Percent change from baseline in weekly focal seizure frequency for each week of the DBP.
To assess the effect of XEN1101 versus placebo on seizure severity and impact in adults with focal epilepsy taking 1 to 3 AEDs in the DBP.	
 Clinical Global Impression of Change (CGI) and Patient Global Impression of Change (PGI-C) scores during the DBP.
CCI	
CCI	
 CCI
CCI	
 CCI

OBJECTIVES	ENDPOINTS
	
• CCI■■■■■
CCI	
• CCI■■■■■

OBJECTIVES	ENDPOINTS
CCI	
CCI	
CCI
CCI	
CCI
CCI	
CCI

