8.2.4 GLOBAL IMPRESSION SCALES

The CGI scale ([Forkmann et al., 2011](#); National Institute of Mental Health [NIMH]) will be administered by a trained physician at selected visits as specified in [Table 1a](#) Schedule of Assessments. The CGI-S scale will be administered at selected visits during the OLE, as specified in [Table 1b](#) Schedule of Assessments.

The PGI-C scale (NIMH) will be provided to the patient for completion at selected visits as specified in [Table 1a](#) Schedule of Assessments. The PGI-S will be provided to the patient for completion at selected visits during the OLE, as specified in [Table 1b](#) Schedule of Assessments.

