9.4 STATISTICAL ANALYSES

9.4.1 GENERAL APPROACH

A basic frequentist approach will be taken with this analysis. Efficacy analyses will generally be 1-sided, 0.05-level tests. The primary efficacy endpoint may include multiple hypothesis tests, with study-wide type I error controlled through a closed-testing procedure. In this Phase 2 study, safety endpoints and secondary efficacy endpoints will not be adjusted for multiplicity across endpoints or arms. All analyses will be accompanied by graphical presentations of results including forest, line, and bar graphs.

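### CGI and PGI-C differences are to be described only by medians and Hodges-Lehmann estimates, which move in whole-point steps on a short ordinal scale and can read zero, or disagree, beside a significant ANCOVA

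*Combined protocol and SAP*

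**What the plan says.** Section 3 lists "Clinical Global Impression of Change (CGI) and Patient Global Impression of Change (PGI-C) scores during the DBP" as the endpoint for the secondary objective on seizure severity and impact. No other endpoint stands against that objective.

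Section 9.4.3 gives the test: "Change scores in each dose group will be compared to placebo using an ANCOVA, including for rank of baseline seizure frequency, region" and CYP3A4 inducer use. The next sentence gives the effect measures: "Estimated medians, and Hodges-Lehman estimates statistics for differences, will be calculated". That bullet has no adjusted mean difference, odds ratio, category proportion or confidence interval. The responder (RR50) bullet in the same section does specify odds ratios with 95% confidence intervals.

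Section 9.4.3 closes with "Analysis detail on statistical testing for secondary endpoints will be provided in the SAP". Section 9.4.1 adds "Efficacy analyses will generally be 1-sided, 0.05-level tests" and that "safety endpoints and secondary efficacy endpoints will not be adjusted for multiplicity across endpoints or arms". Section 8.2.4 cites the scales (for example, "The PGI-C scale (NIMH) will be provided to the patient for completion at selected visits") but does not say how many categories they have. No expected effect on either scale is stated.

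**The concern.** The Hodges-Lehmann difference is the median of all pairwise differences between the two arms. On whole-number scores every pairwise difference is a whole number, so the estimate is a whole number apart from rare half-points. It leaves 0 only when at least half of all pairs favour one arm. With few categories many pairs tie, so a real shift can leave it at 0. The arm median also moves in whole points, but it can jump at a different effect size.

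What is at stake is the reporting of a secondary endpoint. The ANCOVA may be significant while the stated difference is 0, or the medians may differ by a point beside a Hodges-Lehmann estimate of 0. Section 4.3 says the study will inform dose selection, and a summary that moves in whole points separates 10, 20 and 25 mg poorly when their effects differ by fractions of a point.

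**Working it through.** **The plan's own figure.** There is none for CGI or PGI-C. The only stated power, 88% in Section 9.2, is for the primary trend test and is not at issue.

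**Inputs.** From the documents: about 100 patients on placebo and on 25 mg, about 50 on 20 mg and on 10 mg (Section 1.1); one-sided 0.05 tests (Section 9.4.1). Assumed: integer scores with lower meaning better, independent patients, no covariates, a proportional-odds shift, and three placebo distributions:

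- 7 levels, clustered: .03, .12, .25, .42, .12, .05, .01
- 5 levels, clustered: .08, .27, .45, .15, .05
- 7 levels, spread: .10, .15, .18, .20, .17, .12, .08

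**What counts as modest.** On the logistic scale d ≈ ln(OR) × √3/π = 0.551 × ln(OR). This gives d = 0.22 at OR 1.5, 0.31 at 1.75, 0.38 at 2 and 0.61 at 3. For comparison, two negative binomial models calibrated to the Section 9.2 median changes, with trend power of 85% and 88%, imply d of 0.31 and 0.41 for 25 mg on seizure frequency. The dispersion had to be assumed, because it is not stated. OR 1.75 to 2 is therefore a similar size.

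**One case by hand (7 levels clustered, OR 2).**

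1. Placebo cumulative probabilities c: .03, .15, .40, .82, .94, .99, 1.
2. Active: 2c/(1 + c) = .058, .261, .571, .901, .969, .995, 1.
3. P(active better) = sum of each placebo probability times the active cumulative probability one level below = .12×.058 + .25×.261 + .42×.571 + .12×.901 + .05×.969 + .01×.995 = .479. Ties are .252 and active worse .270 (rounded).
4. Neither direction reaches .5, so the true Hodges-Lehmann difference is 0.
5. The placebo median is 4 (c passes .5 at level 4) and the active median is 3 (.571 at level 3), a full point apart.
6. The true mean difference is −0.43.

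One population therefore gives 0, −1 and −0.43. At OR 1.5 the mean difference is −0.25 and the Hodges-Lehmann value is again 0, so it does not separate those two effects. At OR 2.5 P(better) is .517 and it jumps to −1, while the mean difference is only −0.56. On the spread scale at OR 2, P(better) is .534, so it reads −1 against a mean difference of −0.67. The steps can overstate as well as understate.

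**Simulation.** 4000 trials per setting, with a one-sided two-sample t-test standing in for the ANCOVA. The last three columns are percentages of significant trials (HL = Hodges-Lehmann). Each cell gives 100 v 100, then 100 placebo v 50 active.

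| Placebo ratings | OR | Significant | HL = 0 | Medians equal | HL = 0 and medians ≥ 1 apart |
|---|---|---|---|---|---|
| 7, clustered | 1.5 | 47 / 36 | 89 / 75 | 23 / 16 | 58 / 50 |
| 7, clustered | 2 | 84 / 68 | 64 / 50 | 4 / 4 | 58 / 41 |
| 7, clustered | 3 | 100 / 96 | 12 / 15 | 1 / 2 | 10 / 13 |
| 5, clustered | 1.5 | 47 / 34 | 96 / 87 | 72 / 46 | 18 / 29 |
| 5, clustered | 2 | 85 / 70 | 82 / 73 | 24 / 19 | 52 / 45 |
| 5, clustered | 3 | 99 / 97 | 31 / 31 | 1 / 2 | 30 / 27 |
| 7, spread | 1.5 | 49 / 36 | 20 / 2 | 8 / 7 | 15 / 1 |
| 7, spread | 2 | 87 / 73 | 8 / 1 | 4 / 3 | 6 / 1 |
| 7, spread | 3 | 100 / 97 | 0 / 0 | 3 / 2 | 0 / 0 |

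Half-point Hodges-Lehmann values occurred in at most 0.3% of significant trials.

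**Other assumed shapes (100 v 100; OR 1.75 / 2 / 2.5 / 3), HL = 0 among significant trials.** Typical 7-point: 72 / 54 / 25 / 8%. 7-point concentrated at no change: 98 / 93 / 71 / 43%. 5-point: 89 / 82 / 54 / 27%. Another spread 7-point shape: 29 / 20 / 6 / 2%, and 44% at OR 1.5. In these four shapes the medians were equal in 8%, 52%, 43% and 34% of significant trials at OR 2.

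**The case against.** Several objections are sound.

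- A reader might infer that the planned difference will usually be zero. The documents do not support that: they give no number of categories, distribution or expected effect, and the result depends on all three.
- A reader might infer that the medians fail in the same way. They do not. In the two clustered distributions at OR 2 they are equal in only 4% to 24% of significant trials, because the median jumps a full point. Their fault is coarseness and disagreement with the Hodges-Lehmann value.
- A reader might infer that the size of benefit could not be read at all. That is too strong. An ANCOVA can yield adjusted mean differences, Section 9.4.1 promises graphs with all analyses, and Section 9.4.8 promises patient-level listings.
- A reader might infer that the ANCOVA is the wrong model. The point concerns the effect estimate. Replacing or demoting the test is a separate and debatable preference, and a proportional-odds model brings its own assumption, which the simulation builds in and does not test.

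The appeal to a later SAP stands only in part. Section 9 calls itself a summary, and a SAP may add estimates that are not visible here. But the deferral in Section 9.4.3 concerns statistical testing, whereas the effect measures are already stated, so a SAP that follows the protocol inherits them. That an ANCOVA could yield a mean difference does not commit the plan to reporting one.

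**Conclusion.** The point holds as a reporting weakness. The protocol names two effect summaries for CGI and PGI-C, and on a scale of about 5 to 7 categories both move in whole-point steps.

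At odds ratios of about 1.5 to 2, with ratings clustered near the middle, the Hodges-Lehmann difference is exactly 0 in about 50% to 98% of significant comparisons. In the two clustered distributions tabulated, 18% to 58% of significant comparisons pair a Hodges-Lehmann value of 0 with medians at least a point apart. With widely spread ratings the zero rate is below about 30% from odds ratio 1.75 up (as high as 44% at 1.5). At odds ratio 3 it is about 30% or less, except for 43% when ratings are concentrated at no change.

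These figures rest on the assumed category counts, placebo distributions and proportional-odds shift, and on a t-test in place of the covariate-adjusted ANCOVA. The whole-point behaviour itself follows from the definitions. The endpoint is secondary and unadjusted for multiplicity. The primary test, testing hierarchy and sample size are unaffected, so this is a worthwhile improvement and not a flaw that threatens the trial's conclusion.

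**What to change.** Keep the ANCOVA as the test. In place of the Hodges-Lehmann estimate as the main effect measure for CGI and PGI-C, specify one of the following for each dose against placebo:

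- the ANCOVA adjusted mean difference with 95% CI, which comes from the model already planned; or
- a common odds ratio with 95% CI from a proportional-odds model with the same covariates (rank of baseline seizure frequency, region, CYP3A4 inducer use).

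With either, tabulate the number and percentage of patients in each category by arm, and state in the SAP the number of categories and their coding. Medians can remain as description.

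The cost is a few lines of SAP wording and slightly more analysis work. If the odds ratio is chosen, it adds one model per scale and a check of proportional odds. No data collection changes.

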9.4.4 SAFETY ANALYSES

Overall safety evaluations will be descriptive and based on the Safety Population. Graphical and tabular displays will be presented by arm. Safety will be assessed similarly, but separately in the DBP and OLE based on the Safety Population and OLE Safety Populations, respectively.

9.4.4.1 EXPOSURE

Complete dosing experience for all participants in the DBP will be listed, summarized, and presented graphically by arm including the total number of doses given and cumulative dose over time. All dropouts and the associated cumulative dose and arm will also be presented. Exposure in the OLE will be presented similarly to the DBP but will be cumulative including exposure from the DBP.

9.4.4.2 ADVERSE EVENTS

All AE data will be summarized, sorted by system organ class and preferred term assigned by Medical Dictionary for Regulatory Activities (MedDRA) and presented by arm. The following summaries will be provided:

- Listings of all AEs.
- Listings of all SAEs.
- AEs leading to discontinuation of study drug.
- AEs leading to study withdrawal.
- Treatment-related AEs.

9.4.4.3 LABORATORY FINDINGS

The number of participants with substantial changes from baseline will be summarized and presented by arm and visit. Criteria for substantial change will be provided in the SAP. Substantial changes deemed clinically significant by the investigator will be recorded as AEs. Summary statistics for each laboratory value and change from baseline for each visit will be presented by arm in tables and figures such as box plots and mean-plots over time.

9.4.4.4 ELECTROCARDIOGRAMS

All ECG measures will be listed. The number of participants found to have an abnormal ECG, confirmed on a repeat ECG will be summarized and details of abnormalities will be listed by arm.

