8.3.3 ELECTROCARDIOGRAPHIC MEASUREMENTS

A 12-lead ECG will be performed at selected visits as specified in [Table 1a](#) and [Table 1b](#) Schedule of Assessments. ECG printouts will be filed in the patient's source documents for medical safety reviews.

Each ECG recorder will be set-up to the required technical specifications and containing the information required to identify the records. Each ECG recording will be clearly identified (patient identification [ID], visit date, and the actual times of ECG recordings).

Twelve-lead ECG recordings will be taken after the patients have been resting in a semi-supine position for at least 10 minutes. The patients will avoid postural changes during the ECG recordings and site staff will ensure that patients are awake during the ECG recording.

All recorded ECGs will be reviewed by the investigator or medically qualified designee, and the review will be documented in the source. If a patient shows an abnormal ECG, a repeat ECG will be conducted. A cardiologist review of abnormal ECG tracings will be requested if deemed necessary by the investigator.

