8.3.6 PK BLOOD SAMPLES

Blood samples for plasma concentration analysis will be collected during the study for a population PK evaluation of XEN1101. The dates and times of the last dose of background AED(s) and study drug intake, and the blood sample collection dates and times will be recorded on the eCRF. A subset of up to 40 patients may be requested to provide additional PK samples after providing informed consent to more fully define the PK profile of XEN1101.

A separate population PK analysis plan will be generated to support the population PK analysis in focal epilepsy patients. The population PK will be characterized by nonlinear mixed-effects modeling. A separate report to the clinical study report will be written to cover the population PK analysis.

The relationship between XEN1101 plasma concentration and QTcF, predefined efficacy, and AEs will be investigated in a population PK/PD exposure-response analysis. A separate report to the clinical study report will be written to cover the PK/PD analysis.

Plasma PK samples may also be used for other tests, such as profiling of drug binding proteins, bioanalytical method validation purposes, stability assessments, metabolite assessments, and/or to assess other actions of XEN1101 with plasma constituents. Assessment of the plasma levels of background AEDs and potential changes with co-administration of XEN1101 may also be investigated.

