8.4 ADVERSE EVENTS AND SERIOUS ADVERSE EVENTS

8.4.1 DEFINITION OF ADVERSE EVENTS

An AE is any unfavourable and unintended sign (including a new clinically significant abnormal laboratory finding), symptom, or disease temporally associated with the use of a medicinal product, whether or not considered related to it.

An AE may be:

- A new symptom or medical condition.
- A new diagnosis.
- An inter-current illness or an accident.
- A worsening of a medical condition/diseases existing before the start of the clinical trial.
- The recurrence of a disease.
- An increase in frequency or intensity of episodic diseases.
- A clinically significant change in a laboratory or other clinical test parameter that is considered to be an AE by the investigator or sponsor.

An AE does not necessarily include the following:

- An abnormal test that needs repeating, in the absence of accompanying symptoms, and/or any requirement for additional diagnostic testing or medical/surgical intervention. Any abnormal test result that is determined to be an error does not require reporting as an AE.

- Recurrence of the patient's normal seizures are not considered an AE; however, occurrence of status epilepticus or other seizures requiring hospitalization will be counted as an SAE.

Surgical procedures themselves are not AEs; they are therapeutic measures for conditions that require surgery. The condition for which the surgery is required may be an AE. Planned surgical measures permitted by the clinical trial protocol and the condition(s) leading to these measures are not AEs, if the condition leading to the measure was present before inclusion in the trial and has not worsened. In the latter case, the condition should be reported as medical history.

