9.4.4.6 VITAL SIGNS

The number of participants with substantial changes from baseline will be summarized and presented by arm and visit. Criteria for substantial change will be provided in the SAP. Substantial changes deemed clinically significant by the investigator will be recorded as AEs. Summary statistics for each vital sign and change from baseline for each visit will be presented by arm in tables and figures such as box plots and mean-plots over time.

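### The ECG analysis in Section 9.4.4.4 has no baseline reference and no by-arm change summary, so it does not match the primary safety endpoint of clinically significant ECG change

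*Combined protocol and SAP*

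**What the plan says.** Section 3 lists "Clinically significant changes in 12-lead ECG" in the double-blind period among the primary safety endpoints, and the synopsis agrees.

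Section 9.4.4.4 is the whole of the stated ECG analysis. It has three parts:
- a listing of everything measured ("All ECG measures will be listed");
- a listing of the details of abnormalities by arm;
- one summary ("The number of participants found to have an abnormal ECG, confirmed on a repeat ECG will be summarized").

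On how a repeat arises, Section 8.3.3 says "If a patient shows an abnormal ECG, a repeat ECG will be conducted". It gives no interval and no number of repeats.

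The neighbouring sections go further. For laboratory tests, Section 9.4.4.3 says "Summary statistics for each laboratory value and change from baseline for each visit will be presented by arm". For vital signs, Section 9.4.4.6 says "Summary statistics for each vital sign and change from baseline for each visit will be presented by arm". Both also count participants with substantial changes, under criteria to be set in the SAP.

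QTcF is taken up in one other place, Section 8.3.6: "The relationship between XEN1101 plasma concentration and QTcF, predefined efficacy, and AEs will be investigated in a population PK/PD exposure-response analysis". That work is to be reported separately from the clinical study report.

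**The concern.** The endpoint is a change, and a clinically significant one. The planned count is of abnormal tracings that were seen again on repeat. Nothing in Section 9.4.4.4 says that the abnormality must be new since baseline, and nothing says what makes it clinically significant. The one tabulated ECG quantity is therefore not the endpoint.

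The second gap is the absence of any summary of the measurements themselves. The protocol treats QTcF as a risk: Section 5.2 excludes patients above 450 ms at baseline, and Section 7.2 has a withdrawal criterion at 500 ms. Section 4.3 says that the results will guide the dose for confirmatory trials. A modest rise in QTcF with dose matters for that choice. If most patients stay within normal limits, a count of abnormal tracings is a poor way to see it.

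**Working it through.** The plan states no figure for ECG: no expected rate, no SD and no test. There is nothing to reproduce, and the main check is a comparison of texts.

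**Step 1. The measured safety variables side by side (Sections 9.4.4.3 to 9.4.4.7).**

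| Variable | Summary by visit and arm | Change from baseline | Criteria for a notable change |
|---|---|---|---|
| Laboratory (9.4.4.3) | yes | yes | deferred to the SAP |
| ECG (9.4.4.4) | no | no | none given, none deferred |
| C-SSRS (9.4.4.5) | yes | yes | none given |
| Vital signs (9.4.4.6) | yes | yes | deferred to the SAP |
| AUA index (9.4.4.7) | yes | not stated | none given |

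ECG is the only one of the five with no by-visit summary. It also lacks the sentence, present for laboratory tests and vital signs, that clinically significant substantial changes are recorded as adverse events.

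**Step 2. Are the data there?** Table 1a and Section 8.1 schedule ECGs at screening, Day -56, Day 0 before dosing, and Days 14, 28 and 56. Change from baseline at three on-treatment visits needs no new collection.

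**Step 3. What would the planned table show for a shift within normal limits?** Take a patient whose QTcF moves from 410 to 416 ms (illustrative values). Both lie below the protocol's own 450 ms limit. If neither tracing is read as abnormal, no repeat is triggered and the patient adds nothing to the count, whatever the arm.

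**Step 4. Which way does the count err?** For an arm of n patients, let p be the proportion with a new abnormality, c the proportion of those confirmed on repeat, and q the proportion with a pre-existing abnormality that is also confirmed. Then:

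- expected planned count = n × (p × c + q)
- number with a new abnormality = n × p

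All rates below are assumptions, with p = 5%:
- n = 100, c = 50%, q = 0: planned count 100 × 0.05 × 0.5 = 2.5 against 5, so 2.5 too few.
- n = 50, c = 50%, q = 0: planned count 1.25 against 2.5, so 1.25 too few.
- n = 100, c = 100%, q = 0: planned count 5 against 5, so no error.
- n = 100, c = 100%, q = 5%: planned count 100 × (0.05 + 0.05) = 10 against 5, so 5 too many.

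Pre-existing abnormalities are possible. Exclusion criterion 15 removes only those that the investigator judges to preclude participation.

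**Step 5. What would a change summary deliver?** Arm sizes are from the synopsis: about 100 on placebo, 100 on 25 mg, and 50 each on 20 mg and 10 mg. The SD of QTcF change is assumed to be 10 to 20 ms.

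Half-width of the 95% CI for a difference in mean change = 1.96 × SD × √(1/n₁ + 1/n₂)

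| Assumed SD | 25 mg v placebo (100 v 100) | 20 mg or 10 mg v placebo (50 v 100) |
|---|---|---|
| 10 ms | 1.96 × 10 × √0.02 = 2.8 ms | 1.96 × 10 × √0.03 = 3.4 ms |
| 15 ms | 4.2 ms | 5.1 ms |
| 20 ms | 5.5 ms | 6.8 ms |

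**The case against.** There are five fair replies.

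- **Confirmation is sensible.** A repeat screens out artefact, and the endpoint concerns clinically significant changes only. This stands, and the confirmed count should be kept. A reader might infer that the endpoint is undercounted. The documents do not support that: Step 4 shows that the count can err either way, and no rate is given to fix the size.
- **Adverse events are another route.** Section 8.4.1 allows as an adverse event "A clinically significant change in a laboratory or other clinical test parameter that is considered to be an AE by the investigator or sponsor", and Section 9.4.4.2 presents adverse events by arm. A reader might infer that a transient abnormality vanishes from every by-arm count, and that is too strong. But the route depends on individual judgement. Section 8.4.1 also says that an abnormal test needing a repeat, without symptoms or further action, is not necessarily an adverse event.
- **QTcF is modelled against concentration.** Section 8.3.6 does plan this, so QTcF is not ignored. It is a separate report, it is not a comparison of each dose with placebo, and it names no other ECG interval.
- **The Safety Review Committee sees ECGs.** Section 9.4.6 says so. That review is blinded unless it raises a concern, and it is not part of the final by-arm analysis.
- **A fuller SAP is announced.** Section 9 describes itself as a summary, and no separate SAP text is in the documents supplied. The supportable wording is therefore that these summaries are not specified in Section 9.4.4.4, not that they will never be produced. Even so, the laboratory and vital-sign sections commit to change summaries in the protocol itself and point to the SAP for criteria. The ECG section does neither.

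**Conclusion.** The point holds as a gap in specification. Section 9.4.4.4 does not tie its count to baseline or to clinical significance, and it specifies no change-from-baseline summary by visit and arm. Followed as written, a dose-related QTcF shift within normal limits would appear in no by-arm ECG table. Listings, adverse event reporting, blinded review and the exposure-response report do not replace that comparison.

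The size of any error in the count cannot be derived from the documents, and its direction is open. The half-widths of 2.8 to 5.5 ms and 3.4 to 6.8 ms rest on an assumed SD of 10 to 20 ms. They show only the precision that a mean comparison could offer. A reader might want to express the loss as power, but Section 9.4.4 makes safety descriptive and no ECG test is planned, so a power figure would describe nothing in this plan. It would also be wrong to assume that the repeat is taken within minutes, because Section 8.3.3 sets no interval.

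The efficacy analysis and type I error are not affected.

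**What to change.** In Section 9.4.4.4, or in the SAP with a cross-reference:

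1. Apply the rule of Sections 9.4.4.3 and 9.4.4.6 to ECG. Give summary statistics and change from baseline for heart rate, PR, QRS and QTcF by visit and arm, with descriptive 95% CIs for each dose against placebo. State which pre-dose tracing is the baseline.
2. Count patients by arm in post-baseline QTcF categories, both by absolute value (the protocol's own 450 and 500 ms are natural cut points for reporting) and by increase from baseline, with cut points fixed before unblinding.
3. Count post-baseline abnormalities by arm in two rows, with and without repeat confirmation, and show separately those already present at baseline.
4. Say how a clinically significant ECG change is identified, so that one row corresponds to the endpoint in Section 3.

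The cost is a few more tables. ECG measures are already collected and listed, though the sponsor should confirm that each interval is held as a number in the database, since the protocol names only QTcF. The downside is that some artefacts will appear in the unconfirmed row. Printing the confirmed row beside it keeps that visible.
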